## 5.5. Prior and Concomitant Medications

### 5.5.1. Concomitant Medications

As of 30 March 2020, limited clinical drug-drug-interaction studies have been conducted with GS-4224.

In vitro data suggest that GS-4224 is a potential inhibitor of P-glycoprotein (P-gp), cytochrome P450 enzyme (CYP)2B6, CYP2C8, CYP2C9, CYP2C19, CYP3A, uridine diphosphate glucuronosyltransferase 1A1 (UGT1A1) and organic anion transporting polypeptide (OATP)1B1/3. In the absence of clinical data, administration of sensitive substrates of, or narrow therapeutic index drugs that are metabolized or transported by, these enzymes and transporters is not permitted from 14 days prior to the first dose of GS-4224, during the study period, and through the end of the follow-up visit, unless new data becomes available that would allow concomitant use of drugs described above during the study. Furthermore, in vitro data suggest that GS-4224 may be eliminated by metabolism with contribution by CYP3A and Sulfotransferase Family 2A Member 1 (SULT2A1), and may be a substrate of P-gp and breast cancer resistance protein (BCRP) transporters. In the absence of clinical data, administration of strong or moderate inhibitors or inducers of these enzymes and transporters is not permitted from 14 days prior to the first dose of GS-4224, during the study period, and through the end of the follow-up visit.

Examples of medications which are prohibited 14 days prior to the first dose of study drug, during the study period and through the end of the follow-up visit are listed in [Table 5-8](#). Administration of the listed medications may be permitted only if the study investigator deems it necessary for the treatment of a condition that emerges during the course of the study and with the approval of the medical monitor.

Preliminary data from a study that evaluated the effect of famotidine on the plasma exposures of GS-4224 indicated no clinically meaningful effect of acid-reducing agents on the PK of GS-4224. Based on these results, subjects can be allowed to concomitantly administer acid-reducing agents. It is recommended that subjects do not exceed the standard doses of the acid-reducing agents that are substrates for enzymes that are potentially inhibited by GS-4224 (eg, rabeprazole 20 mg once daily, lansoprazole 30 mg once daily, omeprazole 40 mg once daily, etc.).

Any medications not on the list should be reviewed with the sponsor prior to and during the study treatment period with GS-4224.

Subjects who are currently taking other prescription or non-prescription medications may still be entered into the study if, in the judgment of the sponsor and the investigator, the medication will not interfere with the study procedures or compromise subject safety and/or PK assessments. In instances where an excluded medication is initiated prior to discussion with the sponsor, the investigator must notify Gilead as soon as he/she is aware of the use of the excluded medication. Vitamins, ibuprofen, acetaminophen (preferred over ibuprofen if both are applicable), and hormonal contraceptive medications are allowed during the study period.

**Table 5-8. List of Agents Disallowed with GS-4224**

Drug Class	Agents Disallowed
Antibiotics	Ciprofloxacin, Clarithromycin, Erythromycin
Anticonvulsants	Carbamazepine, Oxcarbazepine, Phenobarbital, Phenytoin
Antidiabetics	Glimepiride, Glyburide, Repaglinide
Antidepressants	Fluoxetine, Fluvoxamine, Nefazodone
Antifungals	Fluconazole, Itraconazole, Ketoconazole, Posaconazole, Voriconazole
Antimycobacterials	Rifamycins
Antipsychotic	Lurasidone, Pimozide, Quetiapine
Anxiolytics	Buspirone, Diazepam, Triazolam
Cardiac Medications	Amiodarone, Bosentan, Dabigatran Etexilate, Digoxin, Diltiazem, Dronedarone, Eplerenone, Felodipine, Nisoldipine, Propafenone, Quinidine, Ranolazine, Rivaroxaban, Telmisartan, Tolbutamide, Verapamil, Warfarin
Diuretics	Conivaptan
GI Motility Agents	Cisapride
Herbal/Natural Supplements	Chinese herb sho saiko to (or Xiao Shai Hu Tang), Echinacea, Milk thistle (ie, silymarin), St. John's Wort
Other	Aprepitant, Celecoxib, Colchicine, Cyclosporine, Fexofenadine, HMG CoA Reductase Inhibitors ("Statins"), Modafinil, Sildenafil, Tacrolimus, Tadalafil

GI gastrointestinal; HMG CoA 3-hydroxy 3-methylglutaryl coenzyme A

The potential for GS-4224 to prolong the QT interval has not been evaluated. In the absence of clinical data, administration of any drug that is known to demonstrate QT prolongation should not be permitted from 14 days prior to the first dose of GS-4224, during the study period and through the end of the follow-up visit. Administration of a drug that is known to demonstrate QT prolongation may be permitted only if the study investigator deems it necessary for the treatment of a condition that emerges during the course of the study and with the approval of the medical monitor.

All treatments that the investigator considers necessary for a subject's welfare may be administered at the discretion of the investigator in keeping with the community standards of medical care. Concomitant medications include all prescription, over-the-counter (OTC), herbal supplements, and IV medications and fluids. All concomitant medications received within 30 days before the first dose of study treatment through the 30 day follow-up visit should be recorded on the electronic case report form (eCRF). Palliative and supportive care is permitted during the course of the study for underlying medical conditions and management of symptoms.

Surgery for tumor control or symptom management is not permitted during the study. Palliative radiotherapy is permitted to a single lesion if considered medically necessary by the treating physician as long as the lesion is not a RECIST v1.1 defined target lesion and treatment is not administered for tumor control. Study therapy should be held during the course of palliative radiotherapy and should be resumed no earlier than the next scheduled administration of study therapy. The specifics of the radiation treatment, including the location, will be recorded.

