### **6.6.2. PET-CT**

As cHL is a fluorodeoxyglucose (18F) (FDG)-avid lymphoma, PET-CT is recommended to assess disease at baseline and postbaseline, using the Deauville 5-point scale (5-PS) with subassessments to describe the FDG-avidity of disease.

For subjects with cHL, in addition to CT or MRI scan, a baseline PET-CT is required at screening (or within 6 weeks before C1D1 if the scan was performed as part of standard medical practice), Cycle 3 Day 1, and Cycle 5 Day 1.

PET-CT will be used in lieu of a bone marrow biopsy/aspirate to assess bone marrow involvement. Per Lugano 2014 criteria, PET-CT is required to confirm radiographic CR in subjects with bone marrow involvement at screening. Thus, in subjects with bone marrow involvement at screening and at a time point where CR is suspected, PET-CT will be required to confirm CR if CR was not achieved at Cycle 3 and/or 5.

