- Subjects should not present clinical symptoms or signs indicating clinically significant disease progression; no decline in performance status; absence of rapid disease progression or threat to vital organs or critical anatomical sites (eg, CNS metastasis, respiratory failure due to tumor compression, spinal cord compression) requiring urgent alternative medical intervention; no significant, unacceptable or irreversible toxicities related to study treatment.

For subjects with cHL, Lugano 2014 response criteria should be used {[Cheson 2014](#)} [[Appendix 7](#)].

For additional details and instructions regarding imaging requirements, refer to the study imaging manual.

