**Appendix 7. Response Assessment for Classic Hodgkin Lymphoma (Lugano Classification)**

Revised Criteria for Response Assessment		
Response and Site	PET-CT–Based Response	CT-Based Response
Complete	Complete metabolic response	Complete radiologic response (all of the following)
Lymph nodes and extralymphatic sites	Score 1, 2, or 3* with or without a residual mass on 5PS†  It is recognized that in Waldeyer’s ring or extranodal sites with high physiologic uptake or with activation within spleen or marrow (eg, with chemotherapy or myeloid colony-stimulating factors), uptake may be greater than normal mediastinum and/or liver. In this circumstance, complete metabolic response may be inferred if uptake at sites of initial involvement is no greater than surrounding normal tissue even if the tissue has high physiologic uptake	Target nodes/nodal masses must regress to < 1.5 cm in LDi  No extralymphatic sites of disease
Nonmeasured lesion	Not applicable	Absent
Organ enlargement	Not applicable	Regress to normal
New lesions	None	None
Bone marrow	No evidence of FDG-avid disease in marrow	Normal by morphology; if indeterminate, IHC negative
Partial	Partial metabolic response	Partial remission (all of the following)
Lymph nodes and extralymphatic sites	Score 4 or 5† with reduced uptake compared with baseline and residual mass(es) of any size  At interim, these findings suggest responding disease  At end of treatment (EOT), these findings indicate residual disease	≥ 50% decrease in SPD of up to 6 target measurable nodes and extranodal sites  When a lesion is too small to measure on CT, assign 5 mm × 5 mm as the default value  When no longer visible, 0 × 0 mm  For a node > 5 mm × 5 mm, but smaller than normal, use actual measurement for calculation
Nonmeasured lesions	Not applicable	Absent/normal, regressed, but no increase

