**Revised Criteria for Response Assessment**

Response and Site	PET-CT–Based Response	CT-Based Response
Organ enlargement	Not applicable	Spleen must have regressed by > 50% in length beyond normal
New lesions	None	None
Bone marrow	Residual uptake higher than uptake in normal marrow but reduced compared with baseline (diffuse uptake compatible with reactive changes from chemotherapy allowed). If there are persistent focal changes in the marrow in the context of a nodal response, consideration should be given to further evaluation with MRI or biopsy or an interval scan	Not applicable
No response or stable disease	No metabolic response	Stable disease
Target nodes/nodal masses, extranodal lesions	Score 4 or 5 with no significant change in FDG uptake from baseline at interim or EOT	< 50% decrease from baseline in SPD of up to 6 dominant, measurable nodes and extranodal sites; no criteria for progressive disease are met
Nonmeasured lesions	Not applicable	No increase consistent with progression
Organ enlargement	Not applicable	No increase consistent with progression
New lesions	None	None
Bone marrow	No change from baseline	Not applicable

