\*A score of 3 in many patients indicates a good prognosis with standard treatment, especially if at the time of an interim scan. However, in trials involving PET where de escalation is investigated, it may be preferable to consider a score of 3 as inadequate response (to avoid undertreatment). Measured dominant lesions: Up to six of the largest dominant nodes, nodal masses, and extranodal lesions selected to be clearly measurable in two diameters. Nodes should preferably be from disparate regions of the body and

should include, where applicable, mediastinal and retroperitoneal areas. Non nodal lesions include those in solid organs (eg, liver, spleen, kidneys, lungs), GI involvement, cutaneous lesions, or those noted on palpation. Nonmeasured lesions: Any disease not selected as measured, dominant disease and truly assessable disease should be considered not measured. These sites include any nodes, nodal masses, and extranodal sites not selected as dominant or measurable or that do not meet the requirements for measurability but are still considered abnormal, as well as truly assessable disease, which is any site of suspected disease that would be difficult to follow quantitatively with measurement, including pleural effusions, ascites, bone lesions, leptomeningeal disease, abdominal masses, and other lesions that cannot be confirmed and followed by imaging. In Waldeyer's ring or in extranodal sites (eg, GI tract, liver, bone marrow), FDG uptake may be greater than in the mediastinum with complete metabolic response, but should be no higher than surrounding normal physiologic uptake (eg, with marrow activation as a result of chemotherapy or myeloid growth factors).

†PET SPS: 1, no uptake above background; 2, uptake  $\leq$  mediastinum; 3, uptake  $>$  mediastinum but  $\leq$  liver; 4, uptake moderately  $>$  liver; 5, uptake markedly higher than liver and/or new lesions; X, new areas of uptake unlikely to be related to lymphoma.

Please reference {Cheson 2014} for further information on Lugano Classifications for cHL.

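### Protocol 5.5.1 bars palliative radiotherapy to target lesions only as RECIST v1.1 defines them, so as written it does not protect Lugano target lesions in cHL subjects

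*Protocol*

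**What the plan says.** The rule is in Protocol Section 5.5.1, in the text after Table 5-8. "Palliative radiotherapy is permitted to a single lesion if considered medically necessary by the treating physician", and only "as long as the lesion is not a RECIST v1.1 defined target lesion and treatment is not administered for tumor control". There are therefore four limits: one lesion, medical necessity, no tumor-control intent, and not a RECIST v1.1 target lesion. Study drug is held during the radiotherapy, and the details, including the site, are recorded.

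cHL is a tumor type of interest for the 1000 mg BID cohort (Section 3.2.1) and for Cohort B1 (Section 3.2.2), with its own entry criterion in Appendix 3. Section 6.6.3 says: "For subjects with cHL, Lugano 2014 response criteria should be used".

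Appendix 7 gives the Lugano criteria. In the CT column, partial response rests on a 50% or greater "decrease in SPD of up to 6 target measurable nodes and extranodal sites". A footnote describes the measured lesions: "Up to six of the largest dominant nodes, nodal masses, and extranodal lesions selected to be clearly measurable in two diameters". In the PET-CT column, partial response is a score of 4 or 5 "with reduced uptake compared with baseline and residual mass(es) of any size".

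SAP Section 5.5 plans a by-subject listing of all radiotherapy.

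**The concern.** A bar on irradiating target lesions keeps the lesions that measure response free of a second active treatment. Three of the four limits reach every subject. The fourth, which does that protective work, is tied to RECIST v1.1, and cHL subjects are not scored by RECIST v1.1. A site following the text could irradiate a Lugano target lesion for pain and remain within protocol. Shrinkage on CT, or reduced uptake on PET-CT, would then count toward a partial response attributed to GS-4224.

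The no-tumor-control limit does not replace the bar. It governs why radiation is given, not what it does to the lesion. The protocol imposes both limits for RECIST subjects, so it evidently did not regard intent as sufficient. The response-confirmation rule (a repeat scan by the same technique at least 4 weeks later) does not help either, because it would re-observe the same irradiated lesion.

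**Working it through.** The point is mainly textual, and the plan gives no figure of its own to reproduce.

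**Does other text close the gap?**
- Section 5.5.3 (prohibited treatments) does not list radiotherapy.
- Appendix 6 discusses previously irradiated lesions, but only for RECIST measurability at baseline. Appendix 7 has no counterpart.
- SAP Section 5.5 lists radiotherapy and gives no rule for response.
- Section 6.10.1 and the synopsis efficacy criteria name RECIST v1.1 and Lugano 2014 together. Section 5.5.1 does not, which suggests an oversight.

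**Does a generous reading close it?** Suppose the bar means any lesion that would qualify as a target under Appendix 6. A node with a short axis of 15 mm or more could then be covered, but the two sets still differ:
- *Size.* A 20 × 12 mm node has a 12 mm short axis and is non-target under Appendix 6. The Appendix 7 footnote asks only that a lesion be among the largest and clearly measurable in two diameters, and its progression row uses a longest diameter above 1.5 cm for an abnormal node. This node could be a Lugano target.
- *Number.* Appendix 6 caps targets at 5 in total and 2 per organ; Appendix 7 allows up to 6.

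**How large must the irradiated lesion be (CT column)?** Let *w* be its share of baseline SPD (sum of products of perpendicular diameters), *r* its fractional fall in product, and *d* the fractional fall in the other targets. The total fall is *w·r* + (1 − *w*)·*d*. Setting this to at least 0.5 gives, for *r* > *d*,

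*w* ≥ (0.5 − *d*)/(*r* − *d*).

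The values of *r* and *d* below are assumptions.

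| Irradiated lesion | Other targets | Calculation | Minimum share |
|---|---|---|---|
| vanishes, *r* = 1 | unchanged | 0.50/1.00 | 50.0% |
| vanishes | fall 10% | 0.40/0.90 | 44.4% |
| vanishes | fall 25% | 0.25/0.75 | 33.3% |
| vanishes | grow 20% | 0.70/1.20 | 58.3% |
| 40×30 to 10×10 mm, *r* = 1 − 100/1200 = 0.917 | unchanged | 0.50/0.917 | 54.5% |
| same | fall 25% | 0.25/0.667 | 37.5% |
| 40×30 to 20×15 mm, *r* = 1 − 300/1200 = 0.75 | unchanged | 0.50/0.75 | 66.7% |
| same | fall 25% | 0.25/0.50 | 50.0% |

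The other CT items must also be met, for example "Spleen must have regressed by > 50% in length beyond normal" where the spleen is enlarged.

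**PET-CT column.** It has no SPD threshold, so no share can be computed. Scheduled post-baseline PET-CT falls only at Cycle 3 Day 1 and Cycle 5 Day 1. With 21-day cycles these are days 43 and 85, 42 days apart. On scheduled scans alone, a confirmed PET-based partial response would have to be present at the first and again at the second. The visible text does not say which column decides a partial response.

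**The case against.** The strongest case against is about weight, and most of it stands.

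- *The purpose of the bar is obvious.* Many sites would apply it to any measured lesion. That is fair, and this is a wording slip in a concomitant-treatment rule more than a flaw in an analysis method. But a rule should not depend on sites reading past its words.
- *Exposure is narrow.* Phase 2 never opened (SAP Section 1), which leaves cHL as one of ten tumor types in a BID cohort of at most 20. Such a subject must also need palliation of a lesion that is a Lugano target. On the CT route it must carry about a third to two thirds of baseline SPD in the cases above.
- *No key endpoint is touched.* The visible primary endpoint is DLT incidence; the visible secondary ones are PK and Cohort B1 safety. The rest of the endpoint list is redacted.
- *The bias runs against the outcome.* The gap could only add responses, and SAP Section 1 says the study stopped because objective efficacy was lacking. Nothing suggests that it influenced that decision.

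A reader might infer three stronger points that the documents do not support:

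1. *That irradiated lesions have no handling rule anywhere.* The visible SAP goes from Section 5.6 to Section 7, and Section 6.6.3 defers imaging detail to a manual that is not among the documents. A rule may exist in either.
2. *That Lugano scoring itself needs a new rule for irradiated lesions.* That would add to Appendix 7 rather than correct an error. Statisticians could reasonably differ on it, and the unseen material may already cover it.
3. *That the reported response rate is inflated by a stated amount.* The number of cHL subjects is not given, and Section 8.6 plans response rates by tumor type and treatment, pooling types with fewer than 5 subjects. No shift can be computed.

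**Conclusion.** The concern holds as a gap in the wording of Section 5.5.1, and it is minor. As written, the target-lesion bar does not protect the lesions that measure response in cHL subjects, and no visible text extends it to them. The generous reading narrows the gap without closing it.

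The consequence is limited to a possible Lugano partial response that partly reflects radiation. Efficacy is descriptive with no formal testing (SAP Section 3.5), the Week 48 primary analysis was dropped (SAP Section 2.1.3), and the report is synoptic. A reader might conclude that some reported response is contaminated. The documents do not show this: they record neither an enrolled cHL subject nor an irradiated target lesion.

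The conclusion rests on the literal reading of the sentence and on the visible text being all that governs palliative radiotherapy.

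**What to change.** In Section 5.5.1, replace the RECIST-only condition with: *not a target lesion under the response criteria used for that subject (RECIST v1.1, or Lugano 2014 for cHL)*. The other three limits stay as they are.

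The cost is one phrase. The downside is small: palliative radiotherapy to a target lesion becomes off-protocol for cHL subjects, as it already is for solid-tumor subjects.

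For the stopped study, check the listing planned in SAP Section 5.5 for cHL subjects. For any found, compare the irradiated site with the target lesions and flag any affected response in the study report. The radiation site is already recorded, so this needs no new collection. If no cHL subject was irradiated on study, the matter closes. The corrected wording should be carried into any later protocol that mixes solid tumors and lymphoma.

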### **5.5.2. Rescue Medications and Supportive Care**

- Subjects should receive appropriate supportive care measures as deemed necessary by the treating investigator including but not limited to the items outlined below.
- Diarrhea: Subjects should be carefully monitored for signs and symptoms of enterocolitis (such as diarrhea, abdominal pain, blood or mucus in stool, with or without fever) and of bowel perforation (such as peritoneal signs and ileus). In symptomatic subjects, infectious etiologies should be ruled out, and if symptoms are persistent and/or severe, endoscopic evaluation should be considered. All subjects who experience diarrhea should be advised to drink liberal quantities of clear fluids or rehydration solutions. If sufficient oral fluid intake is not feasible, fluid and electrolytes should be substituted via IV infusion.
- Anemia: Transfusions may be utilized as clinically indicated for the treatment of anemia but should be clearly noted as concurrent medications or in a transfusion page. Consider a potential immunologic etiology and follow the American Society of Clinical Oncology (ASCO) guidelines for use of erythropoietin or derivatives.
- Neutropenia: Prophylactic use of colony-stimulating factors including Granulocyte Colony-Stimulating Factor (G-CSF), PEGylated (Polyethylene Glycol-Coated) G-CSF, or Granulocyte Macrophage Colony-Stimulating Factor (GM-CSF) is not allowed in this study. Therapeutic use of G-CSF is allowed in subjects with Grade 3-4 febrile neutropenia. Consider a potential immunologic etiology.

- Thrombocytopenia: Transfusion of platelets may be used if clinically indicated. Immune thrombocytopenia purpura (ITP) should be ruled out before initiation of platelet transfusion.
- Anti-infectives: Subjects with suspected or documented infectious complication should receive oral or IV antibiotics or other anti-infective agents as considered appropriate by the treating investigator for a given infectious condition, according to standard institutional practice.
- Adverse events with a potential immunologic etiology (irAEs): follow ASCO or local institutional practice guidelines for identification, evaluation, and management of adverse experiences of a potential immunologic etiology. Depending on the type and severity of an irAE, oral or IV treatment with a corticosteroid should be considered, in addition to appropriate symptomatic treatment of a given condition (see Sections 5.4.3 to 5.4.10 for management algorithms guidance).

